Barthel Index: The Barthel Index or Maryland Disability Index was created in 1965 by Mahoney and Barthel. It is one of the most widely used instruments to determine functional capacity. It is a scale that assesses patients' independence in basic activities of daily living (ABVD). Its application takes between 2-5 minutes as a self-report and up to 20 minutes if it is carried out by direct observation. It assesses 10 ABVD, seven of which are activities related to personal care (eating, washing, dressing, grooming, bowel movements, urination, toilet use) and the other three have to do with mobility (ambulation, transferring, and going up/down stairs). Each activity is scored according to the degree of independence, with values ranging from 0 (total dependence) to 15 (total independence). The maximum score is 100, which would indicate that it is totally independent, while the minimum score is 0 and would indicate that the patient has total dependence. Its interpretation is as follows: 100 points independence, ≤ 60 mild dependence, 40-55 moderate dependence, 20-35 severe dependence and 5-20 total dependence.

Visual Analogue Scale (VAS): on the Visual Analogue Scale EVA, the intensity of pain is represented on a 10 cm line. At one end is the phrase "no pain" and at the opposite end "the worst pain imaginable". The distance in centimeters from the point of "no pain" to the one marked by the patient represents the intensity of the pain. It may or may not have marks every centimetre, although for some authors the presence of these marks decreases their accuracy. The way in which the patient is presented, whether horizontal or vertical, does not affect the outcome. It is the most widely used scale, even in critically ill patients. For some authors it has

advantages over others. The patient needs to have good motor and visual coordination, so it has limitations in the elderly patient and in the sedated patient. A value below 4 in VAS means mild or mild-moderate pain, a value between 4 and 6 implies the presence of moderate-severe pain, and a value greater than 6 implies the presence of very severe pain.

NIHSS Scale: This scale is a tool used to assess the severity of a stroke and its neurological effects. It was developed in 1989. It is used both for the initial assessment of the patient and for follow-up. It is widely used in clinical practice and in research related to cerebrovascular diseases. It is made up of 11 items which assess: the level of consciousness, sensory-motor impairment, language and vision, giving scores to each one according to the degree of impairment. Therefore, the scores will vary between 0 (normal function) and 4 (deterioration). The individual scores for each item are added together to calculate a patient's total NIHSS score. The maximum possible score is 42, with the minimum score being 0. Based on the categorization of the scale, a score of 0 points is considered asymptomatic, a minimum deficit a score of 1; mild deficit a score between 2-5, moderate deficit a score between 6-15, significant deficit values between 16-20 points and severe deficit > 20 points.

European Quality of Life Scale (EQ-5D-5L): is a generic questionnaire on health-related quality of life, developed by the EuroQol Group. It assesses five dimensions: mobility, self-care, usual activities, pain/discomfort, and anxiety/depression, each with five levels of severity (no problems, mild problems, moderate problems, severe problems, and extreme problems or unable to) that describe 3,125 possible health conditions. If in a particular dimension, there are no problems this is represented as level 1, while extreme problems are represented as level 5. Hence, each state of health on the EQ-5D-5L can be described using a five-digit number, where 11111 indicates perfect health and 55555 indicates the worst possible state of health. It also features a visual analog scale (EQ-VAS) where the patient rates their overall health on a vertical scale from 0 (worst imagined health) to 100 (best health imaginable).

Annex II. Development of interventions.

Early symptoms of stroke and recognition of these (10 minutes).

A stroke is a neurological disease that occurs when blood flow to the brain is interrupted. This prevents blood from flowing, which means parts of the brain are damaged and may stop working. A Transient Ischemic Attack is a type of stroke that is also caused by the interruption of blood flow, but temporarily, with symptoms usually lasting a few minutes and the person recovering completely in less than 24 hours.

Some of the most common symptoms of stroke are described below:

- Sudden loss of movement or weakness of the arm, leg, or face, especially when it occurs on one side of the body.
- Sudden vision problems.
- Sudden headache, with no apparent cause.
- Slurred speech: Drooping lip, babbling, inability to find the right words, or not being able to understand what other people are saying.
- Sudden problems walking or loss of balance or coordination.
- Sudden sensation of corking or tingling in the face, arm and/or leg on one side of the body.

Living with stroke: the day-to-day care (30 minutes).

Stroke can leave behind sequelae that affect different spheres of personal performance. Therefore, the essential objective is for the affected person to achieve the maximum autonomy to develop. In general, it is interesting to let them do everything they can on their own and if they can't, involve them in some way in the tasks and daily life. Most recovery is experienced in the first three months after the stroke. Recovery continues more slowly until at least six months, and some people continue to recover slightly into a year. In addition, the pharmacological treatment prescribed in each case must be followed. To prevent another stroke it is very important to continue with all these measures for the rest of life.

The most common difficulties and uses when dealing with them are described below.

Slowing down to process information:

- It is "normal" that everything goes slower.
- There is a change of new rhythms and they are not on a whim, so everyone should be aware of the change.
- Simplify the information you want to convey in a simple and concise way.
- Decrease the amount of information to be transmitted at any given time.
- When doing an activity or action, it is useful to establish or think about an outline of how it is going to be carried out.
- Avoid distractions and noise.
- Maintain a more or less constant level of activation, that is, do not do tasks until exhaustion or rest for long periods.

Concentration difficulties:

- Take many breaks of a few minutes during an activity.
- Choose certain times to carry out more difficult activities.
- Vary the activities to maintain interest in them.

Cognitive impairment:

- Have pre-established routines and time dynamics.
- Have routines with personal utensils, that is, always leave the same belongings in the same place.
- External aid: diaries, blackboards, reminder notes, alarms, reminders.
- Personalized daily, weekly or monthly calendars with schedules of activities, appointments...
- Reduce the amount of information that needs to be remembered.
- Put into practice what has been learned as soon as possible.
- Modify the environment to facilitate recall: write down information, choose a fixed place to, put labels...

A language disorder may also occur. An inability to understand and/or utter any type of adequate language or a speech alteration may occur:

- Simplify the conversation.
- Avoid noise.
- Speak slowly and vocalize.
- Position yourself where you can maintain eye contact.
- Turn your face toward the person.
- Look the person in the eye.
- Do not shout.
- Repeat what you have said if the person does not understand you.

- Use short sentences.

Behaviour:

- Understand that the brain injury may have changed the way you react.
- Reinforce positive behaviors.
- Correct an inappropriate response with tact.
- Do not react to strange and incorrect behavior.

Domestic sphere: daily activities such as dressing, hygiene, elimination or eating will be affected to a greater or lesser extent.

Dress:

- Start by undressing, because it is easier.
- Dress seated.
- Wear loose, loose clothing
- Do not wear clothes that are difficult to close.
- Leave enough time to get dressed.
- Break the task down into smaller steps and help only where you need to.
- Always undress the strong side first and always dress the weak side first.
- Whenever possible do without buttons and/or zippers, wear T-shirts, sweaters, sweatshirts...
- Wear comfortable clothes, loose garments and elastic at the waist.
- Replace lace-up shoes with Velcro shoes.
- Wear shoehorns.

Personal hygiene

- Place grab bars next to the toilet and inside the shower.
- Replace the bathtub with a shower.
- Have a shower seat handy.
- Use soap dispensers instead of bottles.
- Use sponge with handle.
- Put everything you need for the shower within easy reach.
- Use electric shaving machines.
- Use electric toothbrushes.
- Use or manufacture a larger and/or longer handle for the toothbrush.

Feeding:

- Sit up for all meals.
- Stand very straight.
- Keep your head slightly forward.
- Look at food.
- Take small bites and sips.
- Avoid foods with different textures, preferably with homogeneous consistencies.
- Avoid carbonated drinks.
- Stay upright for at least 20-30 minutes after eating to digest food.
- Place food between the teeth, on the stronger side of the person's mouth
- Give him thick liquids and foods with a homogeneous texture.

- The weak arm should rest on the table.
- Use deep plates.
- Use barriers around the plates.
- Make the handle of the cutlery larger if the person has trouble holding it.

Hydration:

- When using a straw, always place it on the strong side of your mouth against your cheek.
- If the person cannot drink from a glass or use a straw, use a syringe.

Elimination:

- Do not drink anything at least an hour before bedtime.
- Protect the mattress with an underpad or similar.
- Go to the bathroom regularly and at scheduled times.
- The color of your urine should be only slightly darker than water, so it can help to know if you need to increase or decrease your water intake.
- Avoid constipation.

People who have suffered a stroke are more likely to fall, so muscle-strengthening and balance exercises are important. It is also important to identify and modify as much as possible those aspects of the home that may pose a greater risk of falls, such as removing carpets, putting plastic chairs in the bathtub or shower, as well as handholds, and wearing shoes with non-slip soles.

Visual disturbances: looking towards the affected side, since with a little training the loss of vision of half of a visual field is compensated by turning the head to look to that same side.

Sensitivity disorder (tingling, unpleasant sensations, or lack of sensitivity to touch): Being especially careful about forming wounds or burns without the person noticing.

Mood management and depression (15 minutes).

It is common for mood alterations, anxiety, emotional lability, apathy, irritability or lack of awareness of the sequelae of the stroke to occur, as well as emotional "ups and downs", which must be understood and managed. Post-stroke depression can manifest itself through a variety of symptoms, including persistent sadness, loss of interest in previously enjoyed activities, changes in appetite and sleep, or even difficulty concentrating. As can be seen, there are depressive symptoms that can be related to other functional spheres and therefore can be easily confused with other types of symptoms.

In the face of these difficulties, it is advisable to:

- Identify and manage early symptoms of depression.
- Understand that mood swings are usually not directed against anything or anyone.
- Identify and avoid situations that systematically cause an altered state. Help identify in which situations you "shoot".
- Leave their own space for the affected person, as they can be overwhelmed with so much protection.
- The patient should not be treated as a sick person.
- It's normal for stroke survivors to cry more easily.

- Minimize frustration when facing a task, intervening as little as possible to ensure the achievement of the objective.
- Look for activities that are rewarding, occupy their time, promote their independence and self-sufficiency as much as possible, sometimes simply with that you can avoid other unwanted behaviors.
- Perform structured exercise programs to relieve symptoms of depression.

It is considered valuable to provide documentary support to the sessions as a summary and future information.

Complete breathing, relaxation, guided meditation and mindfulness workshop (25 minutes)

The workshop will be guided by the primary structure of mindfulness:

[figure not shown]
1. Home - Posture Relaxation
2. Mindfulness - inhale and exhale.
3. Open observation – observing emotions while promoting a curious, non-judgmental attitude
4. Closing - brief reflection.

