The main deficits, disabilities and complications observable after a stroke include paralysis, emotional imbalance, speech and language disorders, visual disturbances, cognitive deficits, physical and mental fatigue, epileptic seizures and pain. The greatest risk factor predicting poor prognosis of ischemic stroke is age, which is directly related to epidemiological data.

Ischemic stroke is the leading cause of acquired disability in adults. Two out of three people affected by a stroke associate difficulties in basic tasks such as showering or bathing without help and in household chores. A high percentage of these people perceive their state of health as fair (37.3%), or bad or very bad (36.5%) and a majority suffer pain or discomfort (62.4%) and difficulties in carrying out their daily activities (59.1%).

The mental health of those who have suffered a stroke is also severely affected, with women and those over 65 scoring significantly worse. It is estimated that between 20 and 50% of stroke survivors develop depressive symptoms at some point, which can have a direct impact on the patient's physical and cognitive recovery. The manifestation of post-stroke depression includes everything from persistent sadness to loss of interest in activities that the patient previously enjoyed, changes in appetite or difficulties concentrating or falling asleep. In the same way, dysphagia, a common complication after an ischemic stroke, is also related to the appearance of depressive symptoms. Other risk factors have been described when it comes to developing symptoms of depression in patients who have suffered a stroke, such as low educational level or low economic level. Early identification and treatment of depression in post-ischemized patients is crucial for improving their quality of life and early rehabilitation.

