5. Assess and compare the risk of bronchoaspiration, the presence of pressure ulcers, swallowing, blood pressure, temperature and glucose level and assess the level of pain.
6. To correlate the cognitive state and the level of depression symptomatology with implemented variables.
7. To reduce the psychological impact of depression in patients who have suffered an ischemic stroke who have received health education.
8. To compare the level of depression symptoms in patients who have suffered an ischemic stroke who received health education with those who did not.

Type of study

It is a quasi-experimental, longitudinal and prospective clinical trial.

Material and methods

Scope of study

For the preparation of this study, the target population was patients who have suffered an ischemic stroke for the first time and were treated by physicians from the Neurology and Neurosurgery Service of the Lucus Augusti University Hospital (HULA).

Definition of the subjects to be studied

A representative sample size of patients who have suffered an ischemic stroke for the first time and treated by physicians from the Neurology and Neurosurgery Service of the HULA will be collected. From this sample, 2 groups will be extracted: the group to which a health education program will be applied and the control group to which this program will not be applied.

Subject selection and withdrawal

Inclusion criteria: anterior or posterior cerebral occlusion, age ≥ 18 years.

Exclusion criteria: intracranial hemorrhage, pregnancy, cognitive inability to participate, non-acceptance to participate in the study and administer questionnaires.

Recruitment and recruitment of participants

Prior to the recruitment process, the required informed consent signed by said participant will be obtained. Next, the variables will be collected. The recruitment of participants will be carried out by the principal investigator and collaborating researchers of the study in the neurology and neurosurgery ward:

- [name]
- [name]
- [name]
- [name]

The tasks "*Bibliographic Review, Study Design, Documentation Presentation, Database Design*" will be carried out by the collaborating researcher [name] supervised and in collaboration with the collaborating researchers [name] and [name].

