According to the Atlas of Stroke in Galicia published by the Spanish Society of Neurology in 2018, the autonomous community of Galicia had a population of 2,701,819 inhabitants. Applying an incidence rate of 187.4 cases per 100,000 inhabitants, according to the IBERICTUS study, 5,064 new cases of stroke are estimated each year in Galicia per 100,000 inhabitants. The province of Lugo has 324,842 inhabitants on 1 January 2024, according to the INE, which, applying the same incidence rate, estimates 609 new cases of stroke per 100,000 inhabitants per year. Considering the proportion of ischemic strokes compared to other types of strokes 80:20, the estimated cases of the same would be 487 new cases in Lugo.

In relation to the calculation of the sample size, the following formula is applied.

$$n = \frac{\left[Z_{1-\frac{\alpha}{2}} \sqrt{2p(1-p)} + Z_{1-\beta} \sqrt{p_1(1-p_1) + p_2(1-p_2)} \right]^2}{(p_1 - p_2)^2}$$

Where:

- P2 (frequency of exposure between controls) = 0.4
- OR=4
- Assuming a 1:1 ratio of controls per case
- n = participants as the minimum sample size.

Assuming the calculations, the representative sample size of stroke patients in the province of Lugo would be 70 patients, 35 patients receiving the intervention and 35 controls.

Primary and secondary variables

Independent variables:

- Socioepidemiological: sex, age (< 65 years, 65-80 years, >80 years), date of ischemic event.
- Clinical Signs: type of stroke, treatment modality (received rt-PA or mechanical thrombectomy according to the candidates' protocol), number of falls, degree of pain, presence of pressure ulcers, genesis of new pressure ulcers, episodes of bronchoaspiration, presence of pneumonia, presence of dysphagia, vital signs (blood pressure, glycemia, temperature).
- You receive health education after a stroke or do not receive health education after a stroke.

Dependent variables:

- Assessment of cognitive status by scoring the Mini Mental State Examination (MMSE) questionnaire.
- Assessment of depression symptomatology by scoring on the Beck questionnaire (BDI) or also called depression self-report inventory.
- Assessment of autonomy and ability to perform in basic activities of daily living by means of a score from the Barthel Index.
- Neurological deficit using the NIHSS scale.
- Assessment of quality of life by scoring on the European Quality of Life Scale.

Instruments

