Annex III. Data collection notebook

Participant ID	Sex	Idade	Windy weather	Date of ischemic event	Event Type	BDI to the inductor	BDI after rt-PA	BDI to high	MMSE to the inductor	MMSE tras rt-PA	MMSE to the high
Participant ID	Barthel	NIHSS	Temperature	TA	Glycemia	Swallowing assessment	Breathing	UPP	Pain (EVA Scale)		

MMSE

Orientation	
What year are we in?	1
What season are we in?	1
What date are we on?	1
What day are we on?	1
What month are we in?	1

Where are we?	1
Province?	1
Province?	1
Nation?	1
City?	1
¿Hospital?	1
Plant?	1
Fixation	
Name three objects at one-second intervals.	
Then ask the patient all three.	3
Score one point for each correct answer.	
Repeat the objects until the patient learns all three.	
Attention and calculation	
Series of seven. Score one point for each correct answer. Stop after five answers. Alternatives: Spell "world" backwards.	5
Memory	
Recall of the three previously learned objects	3
Point to a pencil and clock. Have the patient name them when you point to 2	2
Have the patient repeat, "No yes, no no, no ifs and buts."	1
Have the patient follow three types of command: "Take the paper in your right hand, fold it in half, put it on the floor."	3
Have the patient read and obey the following: "Close your eyes" (written in large print)	1
Have the patient write a sentence of their own choice (the sentence must have a subject and an object to make sense, ignore spelling mistakes when punctuating)	1
Enlarge the drawing below up to 1-5 centimeters per side and have the patient copy it (note a point if all sides and angles hold and if the intersecting sides form a quadrangle)	1
	
Total score	30

BDI

Pessimism	
I'm not discouraged about my future	0
I feel more discouraged about my future than I used to be	1
I don't expect things to work out for me	2
I feel like there's no hope for my future and it can only get worse	3
Sadness	
I don't feel sad	0
I feel sad a lot of the time	1

I feel sad all the time	2
I feel so sad or so unhappy that I can't stand it	3
Failure	
I don't feel like a failure.	0
I've failed more than I should have	1
When I look back, I see a lot of failures	2
I feel that as a person I am a total failure	3
Loss of pleasure	
I get as much pleasure as ever from the things I enjoy	0
I don't enjoy things as much as I used to	1
I get very little pleasure from things I used to enjoy	2
I can't get any pleasure from the things I used to enjoy	3
Feelings of guilt	
I don't feel particularly guilty	0

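### Annex II's syringe line does not ask whether swallowing is the reason a person cannot drink, and nothing in the annex links it to the trial's own swallowing assessment

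*Protocol*

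**What the plan says.** Annex II sets out the content of the health education sessions. Within the day-to-day care session, the Hydration list has two lines. The first is about straw placement: "When using a straw, always place it on the strong side of your mouth against your cheek". The second is the line at issue: "If the person cannot drink from a glass or use a straw, use a syringe".

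The eligibility text reads: "Exclusion criteria: intracranial hemorrhage, pregnancy, cognitive inability to participate, non-acceptance to participate in the study and administer questionnaires". Dysphagia is not among these criteria, and the inclusion criteria ask only for an anterior or posterior occlusion and adult age. The background section describes "dysphagia, a common complication after an ischemic stroke".

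Swallowing is measured in the trial. Objective 5 begins: "Assess and compare the risk of bronchoaspiration, the presence of pressure ulcers, swallowing". The clinical variables include "episodes of bronchoaspiration, presence of pneumonia, presence of dysphagia". The data collection notebook in Annex III has a column headed "Swallowing assessment".

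**The concern.** A person may be unable to drink from a glass or straw for different reasons. Weak grip or a weak side of the face makes the vessel hard to manage. Impaired swallowing makes the fluid itself the problem. The line gives the same instruction in every case and does not suggest asking anyone first.

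What is at stake is patient safety in the education group, because the advice is meant to be carried into daily life. A participant or helper who follows it literally could give fluid by syringe to someone whose difficulty is swallowing. The protocol treats bronchoaspiration as a risk worth assessing, so the subject is within its own field of view. Nothing statistical depends on the line.

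**Working it through.** No arithmetic applies beyond a count, so the relevant places are set side by side.

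1. **The trigger.** The syringe line (Annex II, Hydration) is conditional. Its only condition is inability to use a glass or straw. The cause is not asked.

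2. **Who may meet the trigger.** Dysphagia is neither an exclusion nor ruled out by the inclusion criteria (Subject selection and withdrawal). The background section calls it common, and the variables section records it beside bronchoaspiration and pneumonia. Patients with impaired swallowing can therefore be in the education group.

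3. **Whether the swallowing assessment guards the line.** Swallowing is assessed under objective 5 and has a column in Annex III. The section describing the intervention places the initial collection of variables on admission, before the program, with follow-up 3 and 6 months after it. No action is attached to the result, and no sentence in Annex II refers to it. The assessment is a data item and does not condition the advice.

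4. **What else in Annex II bears on the risk.** The Feeding list directly above Hydration advises sitting up, keeping the head slightly forward, taking small sips, avoiding carbonated drinks, staying upright for 20-30 minutes after eating, and giving thick liquids. Posture, sip size and thickness all concern safer drinking, so they count as partial mitigation. None is attached to the syringe step, and none says to ask a clinician.

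5. **Size.** The text at issue is one of two Hydration lines. The education group is planned at 35 of 70 patients. The protocol gives no figure for how many will have dysphagia, or be unable to use a glass or straw, when the workshops take place. The number affected is therefore between 0 and 35, and the document does not narrow that range.

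**The case against.** The strongest objection is that the protocol nowhere says a syringe is unsafe with impaired swallowing. Recording aspiration and dysphagia as variables does not establish that a syringe causes harm. That stands: the hazard is a clinical assumption and has to be labelled as one. It does not remove the point, because the assumption concerns a risk the protocol sets out to assess and needs no outside figure.

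It can also be said that the neighbouring lines (straw on the strong side, weak arm resting on the table, larger cutlery handles) are about one-sided weakness and handling, so the syringe line was probably written for that. This is plausible, and the text does not show otherwise. A reader might infer that the line sends a syringe to the very people most likely to have a swallowing problem. The documents do not support that, since they do not say why participants would be unable to use a glass or straw.

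Three further inferences should be resisted:

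- A reader might conclude that the trial has no swallowing check. It has one; what is missing is any link from it to this line.
- A reader might contrast the line with the sentence on medication, "In addition, the pharmacological treatment prescribed in each case must be followed", and conclude that Annex II defers to clinicians for drugs but not for fluids. That sentence is adherence advice, followed by a remark on preventing another stroke. It does not place the session's advice under the clinical team's direction, so the contrast carries little weight.
- A reader might extend the point to all the fluid and texture advice. No harm from those lines is shown here.

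Finally, a researcher delivers the sessions in person and could add the caveat aloud. That is possible, but the protocol does not say so.

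**Conclusion.** The point holds in a narrow form. One line in Annex II directs people who cannot use a glass or straw to a syringe without separating a handling or facial-weakness cause from a swallowing cause. Nothing in the annex ties it to the swallowing assessment that the trial collects, although patients with dysphagia are eligible. The Feeding advice above it reduces the risk only in part.

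The conclusion rests on one declared assumption, that a syringe can be unsafe when swallowing is impaired. It claims no rate of harm and no number of patients. It is a cheap patient-safety improvement of the lowest severity, with no bearing on bias, power or analysis.

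**What to change.** Reword only this line. Keep its opening condition (the person cannot manage a glass or straw) and replace the instruction with: *ask the treating team about swallowing before using a syringe*. No other line in Annex II needs to change on this account, and a general clause covering all fluid and texture advice would go further than the point supports.

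The cost is a few more words in the session text and an occasional query to the usual care team. Endpoints, sample size, schedule and analysis are untouched.
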